#### 4. Sources of Research Materials

**To be accessed prior to study:** The patient's medical record will be reviewed for diabetes diagnosis, medications, allergies and other diagnoses that may disqualify patient from participation.

|                               |  |
|-------------------------------|--|
| Blood and Urine Samples       | VO 2 max Exercise Testing       |
| Questionnaires                | Echocardiography                           |
| DEXA                          | Endo-PAT                                   |
| Anthropometric measurements   | Dynapulse measurements                     |
| MRI                           | Electrocardiography                        |
| Accelerometer output x 7 days | Brachial Artery Flow Mediated Vasodilation |
|                               | Carotid Artery Intima-Media Thickness      |

#### 5. Subject Recruitment Plan

Subjects for this study will be recruited from the Barbara Davis Center for Childhood Diabetes with whom the PI and Co-I's have a treatment relationship and from study advertisements. Protected health information will only be accessible after the subject has signed a HIPPA recruitment authorization form, provided by the primary care provider, and a research authorization form, provided on entry to the study. Protected health information will only be accessible by study investigators. The initial patient contact will be made by personnel who have a treatment relationship with the subject.

#### 6. Informed Consent Plan

Appropriately qualified and informed personnel who have completed the COMIRB and HIPPA course requirements will fully explain the study protocol and consent form to the subject and guardian verbally in the language they understand. The explanation will be conducted in a quiet environment with adequate time given for the subject and guardian to review the study procedure before the commencement of the study. Asking the subject to explain the study in their own words will assess the subject's understanding. If non-English speaking subjects are enrolled in the study, the investigators will adhere to Section 10C of the COMIRB Instructions for Clinical Investigators regarding the consent of these subjects. The qualified personnel mentioned above will then obtain written consent from the guardian and assent from the subject, co-signed on the consent form, or in subjects who are 18 years or older, direct consent. The PI will make a good faith effort to obtain both parent signatures. The subject and guardian will be provided a copy of the consent form for better understanding and record purposes.

## 7. Special Consent/Assent Plan

Consent will be obtained from all participants in the study. Following explanation, all subjects below 18 years old will co-sign the consent form in addition to the parents signing the consent form. All subjects age 18 or older will sign the standard consent form.

## 8. Subject Compensation, Incentives and Rewards

Subjects will be paid \$425 in gift cards upon completion of all procedures in this study (Table 5 below). If the subject withdraws before the start of the baseline insulin clamp, they will still receive a \$25 gift card for completion of the screening visit. If the subject begins the baseline insulin clamp and needs to stop for any reason, the subject will be given \$100 in gift cards and will be given gift cards for all subsequent completed visits as outlined below. These payments are similar to the payments being made for each visit type in our currently ongoing adolescent studies.

Subjects that bring their completed log book and medication bottles to visits will receive an additional \$5.00 gift card. If co-enrolled, visits 4 and 8 will be performed by and paid for by the T1DX study rather than EMERALD study.

**Table 5 Subject payment schedule**

| Visit 1 | Visit 2 | Visit 3 | Visit 4 | Visit 5 | Visit 6 | Visit 7 | Visit 8 | Total  |
|---------|---------|---------|---------|---------|---------|---------|---------|--------|
| 25.00   | 25.00   | 50.00   | 100.00  | 25.00   | 25.00   | 50.00   | 125.00  | 425.00 |

## 9. Potential Risks to Subjects

### Blood Samples

The collection of blood samples may result in temporary discomfort, bruising, bleeding, and on rare occasions, infection.

Nationally, the NIH Clinical Center has a guideline of 9ml/kg in 6-8 weeks for pediatric studies. Certain studies at our institution do draws over 7ml/kg in 6 weeks, or up to 7 ml/kg in a single draw, but include iron supplementation. Otherwise, the routine guidelines in our Pediatric CTRC are 3ml/kg for a single draw and no more than 7ml/kg over an 8 week period. Our baseline and interim visits will include 5 ml or less of blood (1 tsp) (HbA1c, Hb, Cr, AST, ALT). The insulin clamp visit now includes 130.8 ml of blood, which includes 10.8 ml to check blood sugar every 5 minutes by glucometer for the 4.5 hour clamp.). Thus, our insulin clamp visit is within the more conservative pediatric CTRC guidelines of 3ml/kg for a single draw for pediatric studies for subjects 26 kg or greater. This is unlikely to exclude many subjects, as we have already excluded pre-pubertal subjects, and subjects with BMI<5% (due to potential undiagnosed illness), those groups likely to be the lightest in weight. Therefore, we will limit recruitment to subjects 26 kg or greater if all studies are performed. In addition, by study design, subjects <5% for weight are excluded as are subjects with anemia, screened by our baseline Hb, further increasing the safety of the study regarding blood draws. The two clamp visits are separated by 3 months, and therefore the significant blood draws are spaced enough apart to also fall within guidelines.

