### **3. Eligibility**

#### **a) Inclusion Criteria**

1. Adolescents 12-21 years of age with type 1 diabetes (defined as having positive GAD, ICA and/or IA2A antibodies as well as insulin requirement)
2. Willing to consent for participation in study
3. Both normal weight (BMI 5-85%) and overweight/obese T1D subjects (BMI > 85%) will be enrolled to allow sub-analysis of the effects of BMI on IR, CVD and response to metformin in T1D.

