#### **b) Exclusion Criteria**

1. Current use of medications known to affect insulin sensitivity: oral glucocorticoids within 10 days, atypical antipsychotics, immunosuppressant agents, metformin or TZD
2. Currently pregnant or breastfeeding women
3. Use of a thiazolidinedione within 12 weeks
4. Severe illness or DKA within 60 days
5. Macroalbuminuria
6. Hemoglobin A1C > 12%
7. Weight > 136.4 kg or < 26 kg, BMI < 5%
8. Creatinine > 1.2
9. Hemoglobin < 9
10. Major psychiatric or developmental disorder limiting informed consent
11. Implanted metal devices
12. Inability to tolerate  $\geq 500\text{mg}$  BID of metformin

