Emergency Response Plan: EKG, echocardiogram and blood pressure measures are performed prior to exercise testing to screen for any heart problems making exercise contraindicated. A physician or trained proctor will be present during the test. The CTRC performs graded exercise testing on a regular basis and is equipped with an oxygen supply and defibrillator. In the event that a patient goes into cardiac arrest during the procedure, the research team will call 911.

Blood Volume: We will use a minimum weight cutoff of 26 kg to remain below the most conservative pediatric CTRC blood drawing guidelines. In addition, we pre-screen subjects with a hemoglobin and hematocrit at their baseline visit, and exclude subjects with anemia. This screening also helps to increase the safety of the blood draw. In addition, the blood planned to be frozen and held could also be omitted if needed to reduce blood volume for a particular subject. Finally, our CTRC has a system to track other studies subjects might enroll in, and we ask during our consent process if the subject has been involved in any other studies in the past 6 weeks to avoid excessive blood drawing.

Pregnancy: Pregnancy is an exclusion criterion in the study and is tested for prior to each DEXA and insulin clamp.

Every effort will be made to decrease the risk of loss of confidentiality by limiting access to protected health information, storing this information in a password protected database, and de-identifying study specimens.

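### The 130.8 ml clamp visit exceeds the 3 ml/kg single-draw limit for every eligible subject under 43.6 kg, although the protocol claims compliance from 26 kg

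*Combined protocol and SAP*

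**What the plan says.** Section V.9 (Potential Risks to Subjects, Blood Samples) gives the volume: "The insulin clamp visit now includes 130.8 ml of blood". Of this, 10.8 ml is for the five-minute glucose checks. It gives the limits as well: "the routine guidelines in our Pediatric CTRC are 3ml/kg for a single draw and no more than 7ml/kg over an 8 week period". It then concludes that the clamp visit is "within the more conservative pediatric CTRC guidelines of 3ml/kg for a single draw for pediatric studies for subjects 26 kg or greater".

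The 26 kg figure is carried into two other places. Section IV.3(b), Exclusion Criteria, lists "Weight > 136.4 kg or < 26 kg, BMI < 5" (the BMI figure is a percentile). Section V.10, Protection Against Risks, presents the floor as the safeguard: "We will use a minimum weight cutoff of 26 kg to remain below the most conservative pediatric CTRC blood drawing guidelines". The same paragraph of V.10 allows the blood kept for future research to be left out for an individual subject if necessary.

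The inclusion criterion on age is "Adolescents 12-21 years of age with type 1 diabetes". The clamp is done twice, at Visits 4 and 8.

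**The concern.** The protocol gives the volume, the limit per kilogram and the minimum weight. Any two of these fix the third, and the three do not agree. The claim concerns a limit on blood drawn from participants, many of them minors, and it stands in the risk section on which an ethics board relies. A site that followed the protocol exactly would draw more than the stated limit from its lightest eligible subjects while believing that it complied.

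Two supporting statements in V.9 are also weaker than they read. It says that pre-pubertal subjects are already excluded and that subjects below the 5th percentile for weight are excluded by design. Section IV.3(b) lists neither: it excludes on BMI percentile and on weight below 26 kg, and enrolment starts at age 12.

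**Working it through.** **Inputs**
- Clamp-visit volume: 130.8 ml, of which 10.8 ml is for glucose checks (V.9).
- Single-draw limit: 3 ml/kg. Eight-week limit: 7 ml/kg. National guideline: 9 ml/kg in 6 to 8 weeks (V.9).
- Weight floor: 26 kg (IV.3(b), V.9, V.10).
- Other visits: at most 5 ml each (V.9).
- Blood stored for future research: 16 cc at baseline and at the end of the clamp, read here as 16 or 32 ml per visit (FPLC subsection of IV.5).

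**The glucose-check component.** The insulin infusion lasts 270 minutes with a check every 5 minutes: 270 / 5 = 54 checks, and 10.8 / 54 = 0.2 ml each. This part of the volume is coherent.

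**The stated floor.** The protocol says that the limit is met from 26 kg.
- Allowed at 26 kg: 3 × 26 = 78 ml.
- Drawn per kg at 26 kg: 130.8 / 26 = 5.03 ml/kg.
- Excess: 130.8 − 78 = 52.8 ml, and 52.8 / 78 = 68% over.
- Lowest compliant weight: 130.8 / 3 = 43.6 kg.

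The 26 kg figure is not reproduced.

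**Can another reading of the volume recover 26 kg?** Lowest compliant weight = volume / 3. The rows that omit stored blood assume that it is part of the 130.8 ml, which the protocol does not say.

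| Volume counted | ml | Lowest compliant weight (kg) |
|---|---|---|
| Full visit | 130.8 | 43.6 |
| Without glucose checks | 120.0 | 40.0 |
| Without 16 ml stored | 114.8 | 38.3 |
| Without 32 ml stored | 98.8 | 32.9 |
| Without 32 ml stored and glucose checks | 88.0 | 29.3 |

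No row reaches 26 kg.

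**Can another limit recover it?** At 5 ml/kg the lowest weight is 130.8 / 5 = 26.2 kg, close to the floor, but the protocol states no 5 ml/kg limit. At 7 ml/kg it is 18.7 kg and at 9 ml/kg it is 14.5 kg.

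**Cumulative limits at 26 kg.** One clamp plus the screening and interim visits, even if all fall within eight weeks: (130.8 + 5 + 5) / 26 = 5.4 ml/kg. This is below both 7 and 9 ml/kg. The two clamps are three months apart.

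**The case against.** The strongest reply is that the printed limit, not the volume or the floor, may be the slip. The floor almost matches the current volume at 5 ml/kg, so 26 kg may have been set for this volume under a different rule. The documents cannot settle this. No 5 ml/kg limit appears and 3 ml/kg is printed twice in V.9, so the cause of the mismatch should be left open.

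It is also fair to say that 3 ml/kg is described as a routine and conservative guideline, that the cumulative limits are met at 26 kg, and that V.9 mentions local studies drawing up to 7 ml/kg at once. Those studies give iron supplementation, however, and this protocol provides none. The protocol's specific claim is that it meets the 3 ml/kg limit.

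Several safeguards exist, but none makes the claim true:
- **Calling the clamp a series of draws.** V.9 itself applies the single-draw limit to the whole visit.
- **Omitting stored blood.** This is optional, has no weight trigger, and is not enough at 26 kg. V.9 sets the floor for the case in which all studies are performed.
- **Re-infusing line-clearing blood** (Fasting Morning Insulin Clamp). Whether 130.8 ml is gross or net is not stated. Re-infusion would have to account for 52.8 ml of it.
- **Haemoglobin checks.** Subjects below 9 are excluded or withdrawn, which leaves milder anaemia. Table 2 schedules haemoglobin only at Visits 1 and 5, with none at or after the second clamp.
- **A weight-percentile exclusion.** If applied, it could raise the effective floor, but it is not among the listed criteria.

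What stands is that exposure cannot be quantified and that no endpoint, analysis or power figure is affected.

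**Conclusion.** The concern holds. The clamp volume, the 3 ml/kg single-draw limit and the 26 kg floor cannot all be right. On the stated figures, eligible subjects from 26 kg up to 43.6 kg exceed the limit at both clamp visits, by up to 52.8 ml (68%) at 26 kg. If 32 ml of stored blood is part of the 130.8 ml and is always omitted from lighter subjects, the range over the limit narrows to 26 to 32.9 kg but does not close.

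The conclusion takes 130.8 ml as the blood actually lost at each visit, and takes the single-draw limit as applying to the visit as a whole, as the protocol does. Only the single-draw limit is breached. How many subjects fall in the range is unknown, but nothing in the listed criteria keeps them out. The compliance statement is wrong as written and must be corrected.

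**What to change.** Make the volume, the weight floor and the limit consistent in Sections IV.3(b), V.9 and V.10, so that volume divided by weight is within the stated limit for every eligible subject. The options are:

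1. Keep 130.8 ml and 3 ml/kg, and raise the floor to 43.6 kg (44 kg in round figures).
2. Keep the 26 kg floor and cap each subject's volume at 3 ml/kg, which means at most 78 ml at 26 kg. State which samples are dropped, and in what order.
3. State the limit actually intended, with its justification and any added safeguards such as iron supplementation or a haemoglobin check after the second clamp.

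Whichever is chosen, correct the sentence that claims compliance at 26 kg. State whether stored blood is inside the 130.8 ml and whether that figure is net of re-infused blood. Either add the pre-pubertal and weight-percentile exclusions to Section IV.3(b) or remove the references to them from V.9.

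The choice belongs to the investigators and the ethics board. The cost is a short amendment and, depending on the option, the loss of some of the lightest adolescents or of some samples from them.

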### IV Risks

There is temporary discomfort when the needle goes in and 10% of the time there is a small amount of bleeding under the skin that may produce a bruise. Rarely, there is a risk of a blood clot forming or infection.

**Hyperinsulinemic Euglycemic Clamp:** Hyperinsulinemic euglycemic clamps are the gold standard measure of insulin sensitivity in youth[172]. Surrogate measures of insulin resistance cannot be used in subjects with diabetes. This is because surrogate markers are based on measuring insulin levels in the blood. In all subjects with T1D, exogenous insulin is injected rather than being made by the pancreas. Therefore, a blood insulin level in these groups reflects the amount of insulin injected, not insulin sensitivity. Thus, performing a hyperinsulinemic clamp is necessary to accurately measure insulin resistance in youth, a central question being investigated in this protocol. There is a rare risk of hypoglycemia during the insulin clamp. If blood sugars became extremely low for a prolonged period, this could cause a seizure. To minimize this risk, IV access is obtained prior to insulin administration, and blood sugars will be monitored every 5 minutes throughout the procedure and maintained at 95 mg/dL, to be well above a low level. Two IV's will be in place, in case there is a problem with one IV. If the glucose level is decreasing, glucose will be given to stabilize and return blood sugar levels to normal. IV access will also be left in place until blood glucose values are stable after the study is completed.

During the clamp, there is also a risk of infiltration of the IV solution, which could lead to skin burn or tissue damage. To minimize the risk of any complications with the clamp, during the entire clamp procedure, a pediatric CTRC nurse will remain at the bedside, and a Pediatric Endocrinologist (study Physician) or study Nurse Practitioner or study Physician Assistant will also remain at the bedside. The IV site will be continuously monitored.

Hyperinsulinemic euglycemic clamps with stable isotopes can and have been done safely in diabetic and nondiabetic subjects by the highly experienced investigators in this protocol, in the setting of the highly specialized pediatric CTRC at this institution. We are currently conducting them in adolescents with T1D, T2D obese and lean control youth (PI [name], COMIRB# 06-0665) in the same age group as we now propose. Our current clamp experience at the CTRC by the PI includes approximately 140 clamps overall. Adolescent subjects have tolerated the clamps well and we have had no hypoglycemia and no unanticipated adverse events or serious adverse events to date. In addition, our colleagues at the University of Colorado adult CTRC have performed thousands of hyperinsulinemic euglycemic clamps. Current investigators with adult CTRC clamp protocols include [name] (approximately 100 clamps, only adverse event: superficial thrombophlebitis), [name], PhD (approximately 200 clamps, 1 mild superficial phlebitis/mild arm pain), [name] (approximately 150 clamps, one mild superficial phlebitis), [name] (approximately 150 clamps, no adverse events), [name], PhD 70 clamps (no adverse events), our co-investigator [name] (17 clamps, no adverse events and our co-investigator [name] (10 clamps, no adverse events). Many of the insulin clamp protocols in the adult CTRC use only an RN at the bedside rather than an endocrinologist or specialized NP/PhD like our protocol and check blood sugars only every 10 minutes rather than every 5 minutes like our protocol. Despite these less stringent requirements, of the approximately 800 clamps performed recently by the investigators above, no significant hypoglycemia or severe adverse events have occurred.

### **Tracer Infusions**

This study involves the use of the stable, non-radioactive glucose and glycerol isotopes. These are substances normally present or produced in the body, and thus pose no more risk than typical glucose infusions. There is a theoretical risk of infection from the stable isotope infusions. However, these isotopes are specially produced to be sterile and pyrogen-free by the manufacturer, and in addition, after being reconstituted by the Children's Hospital Colorado Investigational Drug Pharmacy, they are retested for pyrogens and sterility prior to use at the University of Colorado CTRC laboratory and the University of Colorado Clinical Laboratory, respectively, and discarded if not used in the standard expiration period. This is the standard procedure used by numerous studies at the University of Colorado. The stable glucose and glycerol isotopes have previously been determined to be usable for research at our institution (currently being used in our protocols 06-0665 and 07-0988) and others, and an IND is **not** required. To date, we have had no complications from the stable isotope infusions. However, as with any infusion, there is the possibility of infection.

Sterile and pyrogen-free  $^2\text{H}_5$ glycerol and  $6,6\text{-}^2\text{H}_2$  glucose will be obtained in powder form from the manufacturer. The CTRC pharmacist will reconstitute the glucose with sterile technique, filter (0.22 micron) for additional sterilization, aliquot, and freeze at  $-20\text{ C}$  in the CTRC investigational pharmacy freezer. One aliquot is then sent to the CTRC laboratory for confirmatory quantitative pyrogenicity testing and a second aliquot to the Children's Hospital laboratory for anaerobic and aerobic culture to confirm sterility.

### **Metabolic Cart**

The metabolic cart measures the amount of air that the subject breathes in and out. The machine attaches to the subject's mouth through a tube, or a plastic bubble that is placed over the subject's head. There is the potential for experiencing claustrophobia from having the plastic bubble over the subject's head.

### **Magnetic Resonance Imaging**

The MRI is a non-invasive scan of the aorta and calf muscle. MRI uses a magnet and there is no radiation and no risk involved with the MRI. The scan may be loud, therefore the subject is provided with audio protection and optional television.

### **Accelerometer**

The accelerometer will be worn in a pouch that rests on the subject's hip and is positioned upright against the body to measure movement, similar to a pedometer. There is no risk involved with the accelerometer.

### **Study Diet**

There is a small risk for diabetic subjects that blood sugars will be higher or lower than normal at home while eating the study diet as it may differ from the subject's usual diet. To avoid this risk, blood sugars will be checked before and after the meal.

### **Electrocardiography**

The ECG and near infrared spectroscopy device involve adhesive pads, which may cause minor skin irritation.

### **Exercise Test**

The exercise test involves exercising for a short time while the pulse and blood pressure are watched. It is routinely used to diagnose heart and lung problems. Rarely, people get abnormal heartbeats or chest pain while doing this test. There is also a risk of hypoglycemia during exercise in diabetic subjects, which will be minimized by monitoring blood sugars and having snacks and juice available during the exercise testing. The risk of hypoglycemia following the exercise test will be reduced by the provision of a small meal to subjects after completion of the exercise test. Because sedentary and obese subjects are at increased risk of reduced exercise capacity, the results of exercise testing are of potential benefit to subjects.

### **DEXA Scan**

The DEXA scan will measure the percentage of fat and muscle in the participant's body. This procedure will deliver the following amounts of radiation exposure: 10  $\mu$ Sv total body equivalent dose per measurement. The amount of radiation that the participant will be exposed to during the DEXA test is approximately equal to the amount of radiation they would receive being outdoors for one to two days in a high altitude city, such as Denver. Because T1D and sedentary and obese subjects are at increased risk of reduced bone mineral density, the results of the DEXA are of potential benefit to these subjects. **Dynapulse, endo-PAT and Brachial Artery FMD** There may be slight discomfort when the cuff is inflated.

